4.4. Baseline Completion and Registration

Patients will be asked to complete baseline demographic and study questionnaires in-person, over the phone, or via institution-approved video technology with a study staff member at the time of consent, or alternatively via email, telephone, institution-approved video, or mail within two weeks of signing consent. Once baseline measures are complete, patients will be registered for study randomization.

If additional information about palliative care is requested by the patient, the study staff member or clinician may provide any of the following brochures about palliative care: an institutionally approved palliative care brochure produced by the site; the National Institute of Nursing Research brochure *“Palliative Care: The Relief You Need When You Have a Serious Illness”*; or the Center to Advance Palliative Care brochure *“Palliative Care: What You Should Know”*. These brochures are intended to provide additional information for potential study participants who are interested in learning more about palliative care.

DF/HCC institutions will register eligible participants in the Clinical Trials Management System (CTMS) Oncore as required by DF/HCC SOP REGIST-101. Registration must occur prior to the initiation of protocol-specific procedures.

For registration of patients from DF/HCC institutions, study staff will complete the protocol-specific eligibility checklist using the eligibility assessment documented in the participant’s medical record and/or research chart. Study staff will confirm that the participant meets all inclusion criteria as described in this protocol and the criteria on the eligibility checklist.

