5.4. Data Collection

Table 1 depicts the assessments, measurements, and time points for the data collection. We will administer patient-reported measures for 48 weeks from enrollment. We selected a longer administration period in the current study as the median survival for patients with lung cancer is now approximately one year. The study assessment battery takes approximately 20 minutes to complete.

Table 1. Summary of data collection instruments and time-points.

Self-Report Measure	Baseline	Every 6 weeks*	Week 12	Week 24	Week 36	Week 48
Demographic Questionnaire	X					
Self-Administered Comorbidity Questionnaire (SCQ)	X					
Functional Assessment of Cancer Therapy-Lung (FACT-L)*	X	X*	X	X	X	X
Patient Health Questionnaire-9 (PHQ-9)	X		X	X	X	X
Prognosis and Treatment Perceptions Questionnaire (PTPQ)	X		X	X	X	X
Brief Cope	X		X	X	X	X
EuroQol – 5 Dimension (EQ-5D)	X		X	X	X	X
Support Service Utilization Item					X	

*Step 1 patients will complete the FACT-L every 6 weeks for a minimum of 12 months and up to 18 months from enrollment

5.4.1. Data from Electronic Health Record:

Clinical information regarding tumor type (NSCLC, small cell lung cancer, and mesothelioma), current treatment regimen, date of diagnosis of incurable disease,

previous diagnosis of early stage disease, tumor genotype, and ECOG Performance Status will be collected at baseline.

Health care utilization data will be collected after death or at 12-months from the date the last patient enrolled on the study. We will collect data on: (1) outpatient and inpatient PC visits; (2) chemotherapy and radiation therapy administration; and (3) emergency department, hospital and intensive care unit admissions. EOL care measures will include referrals to and length of stay on hospice and location of death.

5.4.2. PC Cost and Resource Utilization Data:

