7.5. Analysis Plan

The primary endpoint of the study is to establish that stepped PC is non-inferior to early integrated PC in QOL, as measured by the FACT-L at week-24. We will begin with descriptive and graphical summaries of the endpoints to evaluate whether the normality assumption is reasonable or if transformation is necessary. Based upon our prior study demonstrating statistical and clinically meaningful between group differences in the FACT-L at 24-weeks, the primary endpoint to compare patient FACT-L scores at week-24 between the study groups using a linear regression model controlling for randomization stratification factors, baseline values, and demographic and clinical factors (as necessary for any imbalances in baseline variables). We will also use linear mixed models of the longitudinal data, allowing us to account for dependency among means over time and to control for demographic and clinical factors when examining change between groups in QOL across multiple time points. We will also compare the number of PC visits between the two groups to ensure that the stepped PC model led to a reduction in PC visits.

We will compare depression (PHQ-9) and coping strategies (Brief Cope, including higher-order factors of the Brief Cope in our sample⁵²: active coping & avoidant coping) at week-24 between groups using linear regression models controlling for randomization

stratification factors, baseline values and selected demographic and clinical factors. We will then evaluate linear mixed models of the longitudinal data, as described above, to examine changes in these outcomes between groups across multiple time points.

To compare illness understanding as measured by the PTPQ between the two groups at week-24, we will analyze appropriate items using the appropriate model for the outcome of interest (e.g., linear regression or generalized linear models with an identity link function and binary response probability distribution) with adjustment for randomization stratification factors and any demographic and clinical factors that are imbalanced to assess differences between groups.

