We will assess the incremental cost-effectiveness of the early integrated PC arm relative to the stepped PC arm from the societal perspective using the average costs and quality adjusted life years (QALYs) accrued under each study arm and as follows: $(\text{Cost}_{\text{early integrated PC}} - \text{Cost}_{\text{stepped PC}}) / (\text{QALY}_{\text{early integrated PC}} - \text{QALY}_{\text{stepped PC}})$.⁶⁵ A \$50,000 per quality-adjusted life-year gained will be considered cost effective.⁶⁶ Costs will include all direct health care costs and indirect (time) costs incurred by patients over their life spans while enrolled in the trial.⁶⁷ The EQ-5D will be used to apply utility weights (quality adjustment) to patients' life spans. Both costs and QALYs will be discounted at a rate of 3%. Based on our prior trials, we expect that few patients will survive past the end of the study period.⁹ Cost and QALY data beyond the end of follow-up for those who are alive will be treated as missing data and estimated using multiple imputation methods. If we find that stepped care is non-inferior to early integrated PC in terms of both QALYs accrued and FACT-L scores, we will ignore QALY data and perform only a cost comparison between the study arms. We will use Monte Carlo methods using 10,000 simulations to incorporate uncertainty in parameter estimates and develop confidence bounds on the estimated cost-effectiveness ratio or the cost difference. Following standard methods of economic evaluation as we have done in other studies, we will also perform parameter-specific sensitivity analyses in which individual parameters are varied singly and in combination, through plausible ranges to assess the relative impact different elements of the program have on overall cost-effectiveness.^{68,69}

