## 6. Outcome Measures

Outcome data included self-report questionnaires collected prior to randomization (baseline) and then again at weeks 12, 24, 36 and 48 (with a  $\pm 2$ -week window) (see Table 1), as well as information collected from the EHR.

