**Table 1. Study Questionnaires**

Self-report measure	Baseline	Every 6 weeks	Weeks 12, 24, 36 & 48	Scoring
Demographics	X			n/a
SCQ	X			Range: 0-45 (higher is worse medical condition)
FACT-L	X	X 	X	Range: 0-136 (higher is better QOL)
PHQ-9	X		X	Range: 0-27 (higher is worse depression)
PTPQ	X		X	n/a

Brief Cope	X		X	Range: 2-8 for each facet (higher is more engagement in coping style)
EQ-5D	X		X	VAS Range: 0-100 (higher is better health state)
Support Service Utilization Item			X 	

 Step 1 patients completed FACT-L every 6 weeks for up to 18 months from enrollment.

 Collected only at week 24.

EQ-5D, EuroQol—5 Dimension; FACT-L, Functional Assessment of Cancer Therapy-Lung; PHQ-9, Patient Health Questionnaire-9; PTPQ, Prognosis and Treatment Perceptions Questionnaire; SCQ, Self-administered Comorbidity Questionnaire.

The primary outcome is patient-reported quality of life at 24 weeks from enrollment, as measured by the FACT-L.

The secondary outcomes are:

1. Patient report of patient-clinician communication about EOL care preference using the following item on the PTPQ: “Have you and your doctors discussed any particular wishes you have about the care you would want to receive if you were dying?” analyzed as “yes” versus “no.” The patient’s final assessment will be used.
2. Length of stay on hospice (in days) among patients who die during the study, as documented in the EHR.
3. PC resource utilization; specifically, the number of outpatient PC visits per patient during the study, as documented in the EHR.

The exploratory outcomes are:

1. Rate of change in quality of life from baseline to week 48, as measured by the FACT-L.
2. Cost-effectiveness as assessed by costs relative to quality adjusted life years. **Note:** Plans for the analysis of cost-effectiveness are not described in this SAP.
3. Patient-reported coping strategies at week 24, as measured by eight subscales of the Brief Cope, including subscales measuring emotional support, positive reframing, active coping, acceptance, self-blame, denial, spiritual coping, and behavioral disengagement, as well as higher-order factors reflecting active coping and avoidant coping).
4. Patient-reported prognostic understanding at week 24, based on relevant items on the PTPQ, including:
  - a. Patient’s primary goal of current cancer care. Responses will be dichotomized based on whether the patient selected “to cure my cancer” versus any of the other options.

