### *Adjustment of the Intervention Effect*

The primary analyses for all outcomes will be adjusted for the randomization stratification variables: study site (MGH vs Duke vs Penn) and cancer diagnosis (NSCLC vs SCLC and mesothelioma). Small strata will be combined as needed to ensure numeric stability of model estimates. If needed, sensitivity analyses will additionally adjust for baseline characteristics that are imbalanced between treatment groups. Imbalanced characteristics will be identified *a priori* by examining the distributions of baseline characteristics known to be associated with the primary and secondary outcomes by intervention group. Characteristics that are imbalanced to an extent that is considered clinically meaningful will be included as adjustment covariates in addition to study site and cancer diagnosis.

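### The cost-effectiveness ratio uses arm-average QALYs with no stated adjustment for baseline EQ-5D utility, although that covariate is collected in both arms before randomization.

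*Protocol*

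**What the plan says.** Protocol 7.5 defines the ratio as the cost difference over the QALY difference, early integrated PC minus stepped PC, "using the average costs and quality adjusted life years (QALYs) accrued under each study arm". EQ-5D supplies the utility weights. No regression model and no covariate is named for QALYs. Uncertainty comes from 10,000 Monte Carlo simulations, and costs and QALYs after the end of follow-up are to be multiply imputed. If stepped PC is found non-inferior on both QALYs and FACT-L, QALYs are set aside and only costs are compared.

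The SAP does not fill this in. In section 6, under the exploratory outcomes, it states: "Plans for the analysis of cost-effectiveness are not described in this SAP". Its general rule in section 8 is "The primary analyses for all outcomes will be adjusted for the randomization stratification variables", meaning site and diagnosis. Other imbalanced baseline characteristics are left to sensitivity analyses, if needed.

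The covariate exists. Table 1 in both documents schedules EQ-5D at baseline and at weeks 12, 24, 36 and 48. SAP section 6 places the baseline questionnaires ahead of allocation: "Outcome data included self-report questionnaires collected prior to randomization (baseline) and then again at weeks 12, 24, 36 and 48". Protocol 4.4 makes them a condition of entry: "Once baseline measures are complete, patients will be registered for study randomization".

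Elsewhere in Protocol 7.5, FACT-L at week 24 is analysed with a "linear regression model controlling for randomization stratification factors, baseline values, and demographic and clinical factors". PHQ-9 and Brief Cope also have their baseline values in the model, and SAP section 9 repeats this for all three.

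**The concern.** A QALY total is survival time weighted by utility. Entry utility is the first point on that utility curve and is likely to predict the later ones. If the arms differ by chance at entry, a difference in simple arm averages inherits part of that gap.

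This matters more for a ratio than for a score difference. The QALY difference is the denominator. The trial expects non-inferior quality of life, and the SAP's sample size assumes a true FACT-L difference of 0, so a small QALY difference is plausible and the ratio may be sensitive to small shifts in it. The same difference helps decide whether a cost-utility or a cost-only result is reported. The Monte Carlo step describes uncertainty around the estimate; it does not re-centre an estimate that an observed imbalance has displaced.

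**Working it through.** The documents state no SD, expected difference or power for QALYs, so there is no planned figure to reproduce.

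**Inputs from the documents**
- 255 per arm, 1:1 (SAP section 7).
- $50,000 per QALY (Protocol 7.5).
- EQ-5D to week 48 and median survival of about one year (Protocol 5.4).
- QALYs accrued over life spans, with imputation beyond follow-up (Protocol 7.5).

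**Assumptions**
- Baseline utility SD 0.15 to 0.25.
- Correlation of baseline with later utility 0.3 to 0.7.
- Exponential survival with median one year.
- No true arm difference.

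**Step 1. Size of a chance imbalance.** SE = SD × √(2/255):
- SD 0.15: 0.0133
- SD 0.20: 0.0177
- SD 0.25: 0.0221

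**Step 2. How much carries through over 48 weeks.** In 4,000 simulated trials (SD 0.20, linear utility path, QALYs truncated at 48 weeks):

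| Correlation | Shift in raw QALY difference per unit of imbalance | Same, adjusted | SE raw | SE adjusted | Variance cut |
|---|---|---|---|---|---|
| 0.3 | 0.459 | −0.009 | 0.0229 | 0.0214 | 1 − (0.0214/0.0229)² = 13% |
| 0.5 | 0.521 | −0.007 | 0.0232 | 0.0214 | 1 − (0.0214/0.0232)² = 15% |
| 0.7 | 0.606 | 0.014 | 0.0238 | 0.0213 | 1 − (0.0213/0.0238)² = 20% |

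Both estimators average about 0, so neither is biased. Adjustment removes the dependence on the imbalance.

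**Step 3. Shift for a one-SE imbalance, 48 weeks.** With carry-through of 0.46 to 0.61, the shift runs from 0.0133 × 0.46 = 0.006 to 0.0221 × 0.606 = 0.013. If only 0.4 carries through, the lower end is 0.0133 × 0.4 = 0.005. At $50,000 per QALY, 0.005 to 0.013 is $250 to $650 per patient. At the edge of the 95% range with SD 0.20, 1.96 × 0.0177 = 0.035; times 0.46 to 0.61 this is 0.016 to 0.021 QALY, or about $800 to $1,050.

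**Step 4. Precision gain.** The share of QALY variance removed equals r², where r is the correlation of baseline utility with total QALYs. Taking r from 0.3 to 0.5 gives 9 to 25%. The simulated 13 to 20% lies inside that range.

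**Step 5. Life-span horizon.** Extending survival past 48 weeks (SD 0.15 to 0.25, persistence of utility 0.6), a one-SE imbalance shifts the QALY difference by 0.012 to 0.034. The SE of that difference grows to 0.10 to 0.12, because variation in survival dominates. The shift is then 0.12 to 0.29 of one SE. Squaring gives 0.12² = 1.4% and 0.29² = 8.4%, so adjustment cuts variance by about 1 to 9%. The upper end lets baseline utility also predict survival.

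**The case against.** The strongest case against has four parts.

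**Silence is not a decision.** A reader might infer that the sponsor chose unadjusted averages. The documents do not say so. Model-adjusted means are also averages, and the SAP leaves this analysis out, so a separate economic plan may specify it. This stands: the supported statement is that no adjustment is pre-specified in these documents.

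**Stratification factors.** A reader might also infer that the economic analysis ignores site and diagnosis because the SAP does not cover it. The text points the other way. Protocol 7.5 treats utilization and cost together, names a stratification-adjusted regression for PC visits, and then refers to the linear regression when discussing cost outcomes. Protocol 7.5.2 says the factors will be considered in analysis, and the SAP's general rule covers all outcomes. This part needs only confirmation.

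**Size.** The documents give no expected QALY difference and no QALY non-inferiority margin. A claim that imbalance would reverse the sign of the ratio, or alter the cost-only decision, therefore has no documented benchmark. On the plan's life-span horizon the shift is a modest fraction of the standard error, and the 9 to 25% variance reduction applies only if QALYs stop at about 48 weeks. This stands as well.

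**Validity.** The raw difference is unbiased over randomizations, and if the Monte Carlo bounds reflect sampling variation they already include chance imbalance. That is correct. What remains is the centring of the estimate given the imbalance that actually occurs, and some precision.

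The comparison with FACT-L is also imperfect, since a QALY total is cumulative and depends on survival, and the PTPQ items are not baseline-adjusted either. It does show that the plan uses baseline adjustment where a baseline score exists for a continuous outcome.

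**Conclusion.** The point holds as a low-cost improvement to an exploratory analysis. It is not an error that invalidates the analysis. The documents name no baseline-utility adjustment for QALYs, and the covariate is available before randomization in both arms. On assumed utility SDs of 0.15 to 0.25, the displacement from a typical imbalance is on the order of 0.01 QALY over 48 weeks. It is larger in absolute terms over life spans but smaller relative to the standard error. The precision gain likewise depends on the horizon, and is small on the horizon that Protocol 7.5 describes. These sizes rest on the assumed SD, correlation and survival model, none of which is in the documents.

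The effect is confined to the QALY difference, the ratio built on it, and the rule that can replace the ratio with a cost-only comparison.

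**What to change.** Add a sentence to Protocol 7.5 or to the separate economic plan, before economic results are seen:
- Estimate the QALY difference by linear regression on arm, baseline EQ-5D utility, site and diagnosis.
- Refit it within each imputed data set and carry the adjusted difference and its uncertainty through each Monte Carlo replicate, into both the ratio and the QALY non-inferiority check.
- Confirm that the cost difference is estimated by regression on arm, site and diagnosis, as the existing text suggests.

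The unadjusted arm averages can still be reported alongside. No new data are needed, because baseline questionnaires must be complete before registration. The cost is one or two sentences and a few lines of code; fixing the choice in advance also removes later discretion over whether to adjust.

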7.3. Exploratory Endpoints

- 7.3.1. To compare the longitudinal patterns in QOL in patients assigned to stepped PC versus early integrated PC, as measured by repeated assessments of FACT-L.
- 7.3.2. To compare the superiority of stepped PC versus early integrated PC with respect to cost-effectiveness.
- 7.3.3. To compare coping strategies in patients assigned to stepped PC versus early integrated PC.
- 7.3.4. To compare prognostic understanding in patients assigned to stepped PC versus early integrated PC.
- 7.3.5. To compare depression in patients assigned to stepped PC versus early integrated PC.
- 7.3.6. To compare health care utilization at the end of life (i.e., emergency department visits, hospitalizations, and chemotherapy administration) in patients assigned to stepped PC versus early integrated PC.

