## **9. Statistical Analysis**

### *Primary Outcome*

The primary outcome is patient-reported quality of life at week 24, as measured by the FACT-L. The difference in week 24 means between intervention groups will be estimated using a linear regression model with group assignment (stepped PC vs early integrated PC) and baseline FACT-L score, as well as randomization stratification factors, as main effects. Using the pre-specified non-inferiority margin of 4.5 points, non-inferiority of stepped PC will be established if the lower limit of the 90% confidence interval (CI) for the estimated difference in means is greater than -4.5. The corresponding p-value for non-inferiority will be calculated using a one-sided test of the estimated difference in means against a null value of -4.5 with a significance level of 0.05. Model-based estimates of the mean with 95% CI in each group, the difference in means between groups and its 90% CI, and the p-value will be reported.

To accompany the approach described above, we will also use a linear mixed effects regression model to estimate the difference in week 24 means between intervention groups. This model will utilize FACT-L scores at baseline, week 12, and week 24, with estimation via maximum likelihood. The model will include fixed effects for group assignment (stepped PC vs early integrated PC), time from baseline (in weeks), time-by-group interaction, and randomization stratification factors, as well as random intercepts for each patient. A contrast will be used to estimate the difference in means at week 24, and this estimate will be evaluated for non-inferiority in the same manner described above. This will be reported as a sensitivity analysis for evaluating non-inferiority for the primary outcome.

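### The economic plan drops QALYs once stepped PC is non-inferior on QALYs and FACT-L, but gives no QALY margin, so a permitted QALY loss can be counted as zero

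*Protocol*

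**What the plan says.** Protocol 7.3 lists the exploratory aim as "To compare the superiority of stepped PC versus early integrated PC with respect to cost-effectiveness". Protocol 7.5 defines an incremental cost-effectiveness ratio (ICER) of early integrated PC relative to stepped PC, and states that $50,000 "per quality-adjusted life-year gained will be considered cost effective". A conditional rule follows: "If we find that stepped care is non-inferior to early integrated PC in terms of both QALYs accrued and FACT-L scores", then "we will ignore QALY data and perform only a cost comparison between the study arms". The 10,000 Monte Carlo simulations are to "develop confidence bounds on the estimated cost-effectiveness ratio or the cost difference". The section also promises that "we will also perform parameter-specific sensitivity analyses in which individual parameters are varied singly and in combination".

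For FACT-L the margin is explicit (SAP, Primary Outcome: "Using the pre-specified non-inferiority margin of 4.5 points"). Margins are also given for end-of-life communication (10%) and hospice stay (7 days). None is given for QALYs, and the SAP's list of exploratory outcomes says "Plans for the analysis of cost-effectiveness are not described in this SAP".

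**The concern.** There are two separate problems.

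- **The trigger is incomplete.** It needs a non-inferiority test on QALYs, but the documents give no margin, significance level or power for one. Whoever later picks the margin also picks which analysis is reported.
- **Passing the test does not show equality.** A non-inferiority result is compatible with a loss, up to a limit set by the margin and the standard error. The cost-only branch prices that loss at zero and drops its uncertainty and its correlation with cost.

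The FACT-L condition does not close the gap. It concerns a single score at week 24, analysed on available data without imputation (SAP, Missing Data), so patients who die before week 24 contribute nothing to it. QALYs in Protocol 7.5 are utility weights applied to patients' life spans, so they include survival and later follow-up. Non-inferiority on the first does not bound a loss on the second.

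At stake is an economic result that could point the opposite way from the plan's own threshold.

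**Working it through.** **The plan's own non-inferiority calculation.** SAP section 7 gives all inputs for FACT-L: margin 4.5, SD 17.5, true difference 0, one-sided alpha 0.05, power 80%. Then n = 2 × (1.645 + 0.842)² × 17.5² / 4.5², which rounds up to 188 per group (power 80.2%). This matches the stated figure. None of these inputs exists for QALYs, so there is no QALY figure to reproduce.

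**Value of an ignored loss.** Value = 50,000 × loss.
- 0.01 QALY: $500 per patient
- 0.03 QALY: $1,500
- 0.10 QALY: $5,000

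**Break-even loss.** Loss = saving / 50,000.
- $500 saved: 0.01 QALY
- $1,000 saved: 0.02 QALY
- $2,000 saved: 0.04 QALY
- $5,000 saved: 0.10 QALY

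For scale, Protocol 5.3.1 expects a median of three PC visits on step 1 against seven with early integrated PC by week 24. Four fewer visits at an assumed $100 to $500 each would save $400 to $2,000, with break-even at 0.008 to 0.04 QALY. This covers visits only; the planned costs are much wider.

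**Two illustrations (assumed values).**
- Saving $1,000, loss 0.03: ICER of early integrated PC = 1,000 / 0.03 = $33,333, below the threshold. Net benefit of stepped PC = 1,000 − 50,000 × 0.03 = −$500. The cost comparison alone shows stepped PC ahead by $1,000. The two disagree.
- Saving $2,000, loss 0.03: ICER = $66,667 and net benefit = +$500. There is no reversal.

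**Which losses can pass.** With all 255 per arm and one-sided alpha 0.05 (assumed by analogy with the other tests), the largest observed loss still declared non-inferior is L = margin − 1.645 × SD × √(2/255). At an assumed QALY SD of 0.3 the standard error is 0.0266:

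| Margin | Largest observed loss L | Value at $50,000/QALY |
|---|---|---|
| 0.03 | none (an observed gain of about 0.014 is needed) | – |
| 0.05 | 0.006 | $315 |
| 0.075 | 0.031 | $1,565 |
| 0.10 | 0.056 | $2,815 |

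**Chance of contradiction.** Take a true loss of 0.03 and a fixed saving of $1,000. The rule contradicts the threshold when the observed loss lies between 0.02 (break-even) and L. The chance is Φ((L − 0.03)/SE) − Φ((0.02 − 0.03)/SE), or zero if L is below 0.02. At SD 0.3 and margin 0.10 this is 0.839 − 0.353 = 0.486.

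| Assumed QALY SD | Margin 0.05 | Margin 0.075 | Margin 0.10 |
|---|---|---|---|
| 0.2 | 2% | 53% | 70% |
| 0.3 | 0% | 17% | 49% |
| 0.4 | 0% | 0% | 24% |
| 0.5 | 0% | 0% | 6% |

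These figures leave out the FACT-L condition, which can only lower them. With a $2,000 saving and SD 0.3, the chance of an observed contradiction is 0% at margins 0.05 and 0.075 and 19% at 0.10. True net benefit then favours stepped PC, so such a result would be sampling error.

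**The case against.** The strongest reply is that the two problems pull against each other: without a margin the cost-only branch cannot be triggered, and the ICER stands. That holds until someone sets a margin. The protocol plainly intends one to be used, and setting it after the data are seen is the worst case.

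Several other points stand:
- The SAP expressly leaves this analysis out, so a margin may exist in an economic plan that was not supplied. The claim is limited to the supplied documents. A margin found elsewhere would still leave the instruction to discard QALYs in place.
- The saving, loss, SD and margin used above are all assumed. Planned costs include inpatient care, drugs and patient time, so even the sign of the cost difference is unknown. A population that mixes roughly one-year median survival with prognoses of several years argues for the larger SDs, where contradiction is less likely.
- The endpoint is exploratory, and both documents say exploratory results will emphasise estimates and confidence intervals. That softens the impact, but it does not require the QALY difference to be shown in the cost-only branch. The generic sensitivity analyses do not require it either.

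Three stronger readings are tempting and not supported:
- A reader might infer that the verdict will reverse. It can, under some combinations only.
- A reader might infer that the trial will declare stepped PC cost-effective on cost alone. Protocol 7.5 promises a cost comparison and does not say what will be concluded from it.
- A reader might infer that the design expects a QALY difference near zero, which would make the ratio unstable. The zero difference in SAP section 7 is for week-24 FACT-L, and no expected QALY difference is stated. A ratio is unstable only if the QALY difference turns out to be near zero.

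**Conclusion.** The concern holds in conditional form. The supplied documents make the economic analysis depend on a QALY non-inferiority test that they do not define, and then discard the QALY result if it passes. The value discarded is $500 per patient for each 0.01 QALY. The cost-only result contradicts the $50,000 threshold exactly when the saving is less than $50,000 times the QALY loss and that loss passes the chosen margin.

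The likelihood cannot be fixed from the documents. With a $1,000 saving, a true loss of 0.03 and 255 per arm, it runs from about 0% to about 49% at SD 0.3 as the margin goes from 0.05 to 0.10. It is about 6% at SD 0.5 and margin 0.10. All of these are upper bounds because FACT-L non-inferiority is also required. The unstated margin is therefore a main determinant of the answer. The change is worth making, but it affects an exploratory endpoint only.

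**What to change.** Delete the sentence in Protocol 7.5 that sets QALYs aside, or override it in the separate economic plan, before costs and QALYs are compared by arm. In every case report:

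- incremental cost and incremental QALYs, each with a confidence interval;
- incremental net monetary benefit of stepped PC at $50,000 per QALY, that is 50,000 × (QALY difference, stepped minus early integrated) − (cost difference, stepped minus early integrated), with a confidence interval;
- an acceptability curve from the 10,000 simulations already planned, with cost and QALYs drawn jointly;
- the cost difference alone as a secondary display.

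Net benefit has no denominator, so it stays well behaved if the QALY difference proves small. Pre-specifying and justifying a QALY margin would cure the undefined trigger, but not the pricing of a permitted loss at zero. If the sponsor keeps a non-inferiority statement on QALYs, it needs a margin and an alpha, and the QALY difference should still be reported.

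The cost is a short text change and a few more summaries of the same simulations. EQ-5D and cost data are already collected.
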